1. SYNOPSIS

Study Title	ToKa HTO Virtual Clinical Trial	
Internal ref. no. / short title	NA	
Study Design	Virtual comparative trial	
Study Participants	Imaging data derived knee OA cohort	
Planned Sample Size	20	
Planned Study Period	12 months	
	Objectives	Endpoints
Primary	Safety comparison between existing HTO device (Tomofix) & ToKa	Calculation of bone and device load environment using Finite Element Analysis (FEA)

2. ABBREVIATIONS

CI	Chief Investigator
CRF	Case Report Form
CTRG	Clinical Trials & Research Governance, University of Oxford
FEA	Finite Element Analysis
GCP	Good Clinical Practice
GP	General Practitioner
HTO	High Tibial Osteotomy
ICF	Informed Consent Form
ICH	International Conference of Harmonisation
NHS	National Health Service
NRES	National Research Ethics Service
PI	Principal Investigator
PIL	Participant/ Patient Information Leaflet
R&D	NHS Trust R&D Department
REC	Research Ethics Committee
OA	Osteoarthritis
SOP	Standard Operating Procedure
TKR	Total Knee Replacement

UKR	Unicompartmental Knee Replacement
-----	-----------------------------------

3. BACKGROUND AND RATIONALE

High Tibial Osteotomy (HTO) is an alternative to knee replacement in suitable patients with early knee osteoarthritis (OA), it is particularly suited to patients with single compartment disease who otherwise would be suitable for unicompartmental knee replacement (UKR)¹. OA of the knee is very common and increasing driven by the ageing of the population². The current limitations of HTO are related to the difficulty of achieving the desired correction due to a challenging surgical technique and soft tissue irritation due to the use of generic stabilisation plates³. This study will examine the safety equivalence of a new patient specific HTO process which has patient specific 3D printed plates, ToKa, with the existing most commonly used HTO procedure using the Tomofix plate. Importantly this study will be undertaken as a *Virtual Trial*, existing anonymised 3D imaging data will be used to create the virtual patient cohort. This cohort will receive both procedures, which for this type of procedure is only possible in a virtual scenario.

The main question to be addressed is: “Is the ToKa procedure as safe as the most commonly used existing HTO procedure?”. In this context safety concerns the mechanical loads placed upon the tibia and the support plate.

The interventions will all be made on computer models, the 3D imaging data will be used to create the intact (un-operated) models of the subject tibias. Each model will then be virtually operated upon, with both the ToKa and Tomofix procedures. The models will then be loaded with physiological loads experienced during function and the mechanical states compared⁴.

In order to build the cohort of virtual patients existing anonymised CT data from patients with knee OA will be used. The exclusion criteria are: previous knee or osteotomy surgery, abnormal anatomy of the tibia, poor quality CT data. This study will use data from 20 patients, allowing paired comparison between each intervention in each virtual patient increasing the study power. There are no previous studies of this type to base a power analysis upon, thus the data will be critically evaluated and should increased numbers be required an extension to the ethics will be made. The study findings will be relevant to a knee OA population.

[figure not shown]
4. OBJECTIVES AND OUTCOME MEASURES/ENDPOINTS

Objectives	Outcome Measures/Endpoints

Primary Objective To investigate whether the new ToKa HTO procedure is as safe as the currently widely used Tomofix HTO
	The key outcome measures are the mechanical load variables describing the mechanical loads present in the tibia and implanted devices during physiological loading as determined by FEA.

5. STUDY DESIGN

The study design is a virtual clinical trial in which BOTH interventions are applied to the virtual population. This is only possible in a virtual scenario. This allows powerful paired analysis.

Flow diagram:

6. PARTICIPANT IDENTIFICATION

6.1. Study Participants

Anonymised CT data sets from patients with moderate to severe knee OA.

6.2. Inclusion Criteria

- Appropriate existing CT data of lower limb.
- Male or Female, aged 18 years or above.
- Diagnosed with moderate to severe OA of the knee.

6.3. Exclusion Criteria

The participant may not enter the study if ANY of the following apply:

- Abnormal anatomy of tibia or presence of pathology other than OA, e.g. bone tumour.
- Previous knee or osteotomy surgery.
- Presence of metal-work.

7. STUDY PROCEDURES

7.1. Recruitment

Data obtained by querying hospital PACS systems for suitable patients with suitable radiological examinations, anonymised by hospital before transmitting to research team.

7.2. Informed Consent

We believe this is not required for anonymous use of existing imaging data.

7.3. Screening and Eligibility Assessment

CT data to be reviewed by surgical member of team to ensure subjects meet the inclusion criteria and that none of the exclusion criteria apply.

7.4. Randomisation, blinding and code-breaking

NA

7.5. Baseline Assessments

Intact tibia models will be loaded with physiological loads to establish a per subject baseline value for mechanical load variables.

7.6. Subsequent Visits

NA

7.7. Discontinuation/Withdrawal of Participants from Study

NA

7.8. Definition of End of Study

The end of study is the date of the final FEA analysis has been performed.

8. INTERVENTIONS

The interventions will all be made on computer models, the 3D imaging data will be used to create the intact (un-operated) models of the subject tibias. Each model will then be virtually operated upon, with both the ToKa and Tomofix procedures. The models will then be loaded with physiological loads experienced during function and the mechanical states compared⁴. The time point for the comparison will be 6 weeks simulated post-operation.

9. SAFETY REPORTING

NA

10. STATISTICS AND ANALYSIS

10.1. Description of Statistical Methods

All study practices and statistical methods are based on the International Conference on Harmonization (IHC) document "Statistical Principles for Clinical Trials."

Data will be summarised by treatment group. Baseline characteristics, and safety outputs total overall columns will be included to summarise all subjects.

For all baseline, demographic, safety and efficacy outputs data will be summarised by treatment group. In summary tables of continuous variables, the minimum and maximum statistics, the arithmetic mean and median, the 95% confidence interval, standard deviation, and standard error will be presented will to the same number of decimal places as the original data.

In summary tables of categorical variables, counts and percentages will be used. The denominator for each percentage will be the number of subjects within the population treatment group unless otherwise specified.

All hypothesis testing will be carried out at the 5% (2-sided) significance level unless otherwise specified.

Two one-sided test (TOST) procedure will be used to test equivalence⁵.

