10.3. Analysis of Outcome Measures/Endpoints

Two one-sided test (TOST) procedure on the mechanical load variables. The primary outcome measure will be maximum mechanical stress (von Mises stress) in the device under physiological loading experienced during gait and stair function at a simulated six weeks post-operatively. The secondary outcome measure will be the maximum mechanical strain (von Mises strain) in the bone around the screws holding the HTO plates.

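### Equivalence is to be tested by TOST, but no margin, scale or decision rule is given for either outcome, so the main test cannot return a verdict

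*Combined protocol and SAP*

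**What the plan says.** Section 3 sets the aim, "This study will examine the safety equivalence of a new patient specific HTO process", and puts the main question as "Is the ToKa procedure as safe as the most commonly used existing HTO procedure". Section 4 repeats it as the primary objective. Section 10.1 then says "Two one-sided test (TOST) procedure will be used to test equivalence", with a citation to a general methods paper on equivalence and noninferiority testing. Section 10.3 applies it: "Two one-sided test (TOST) procedure on the mechanical load variables". The same section makes maximum von Mises stress in the device the primary outcome and maximum von Mises strain in the bone around the screws the secondary outcome. No other test is named.

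Every virtual patient receives both procedures, and section 5 says of this design: "This allows powerful paired analysis". Section 10.2 plans 20 patients, requests 30 records, and says that there was no earlier study on which to base a power analysis. The general level in 10.1 is: "All hypothesis testing will be carried out at the 5% (2-sided) significance level unless otherwise specified".

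No section gives a margin for stress or strain, a scale on which to compare the procedures, a reference limit, or a rule for concluding equivalence.

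**The concern.** A TOST consists of two one-sided tests, each against one end of a margin. Without the margin its null hypotheses are undefined, and there is nothing to reject. The scale matters for the same reason. A margin on the stress difference and a margin on the ToKa/Tomofix ratio are different hypotheses, because a fixed ratio corresponds to a different absolute amount in each patient.

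The study's main safety conclusion depends on this test. The plan has no blinding (section 7.4 is marked not applicable), and section 10.2 provides for evaluating the data before deciding whether more patients are needed. Results could therefore be known while the margin is still open, and nothing in the plan prevents that.

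**Working it through.** **1. Inputs from the plan.** n = 20 pairs (section 10.2), so df = 19. Level: 5% two-sided by default (section 10.1). Margin, SD of the paired contrast, expected difference and target power: none stated. The figure of 20 therefore cannot be reproduced from a power calculation, and the plan does not claim that it can.

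**2. The rule a TOST needs.** With mean paired contrast D, sample SD s and margin M, equivalence is concluded only if

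−M < D − t·s/√n and D + t·s/√n < M.

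The data supply D, s and n, and the level supplies t. M is missing, and so is the scale on which D and s are computed.

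**3. Width of the interval.** When s equals SDd, the half-width is t/√20:
- 5% per side (90% CI): 1.729/4.472 = 0.387 SDd
- 2.5% per side (95% CI): 2.093/4.472 = 0.468 SDd

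**4. Power over assumed margins.** Let m = M/SDd, let d be the true difference in SDd units, and let u = s/SDd, where 19u² follows a chi-square distribution on 19 df. Then

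power = ∫ [Φ((m − d)√n − t·u) − Φ((−m − d)√n + t·u)] f(u) du, for u from 0 to m√n/t.

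For n = 20 and d = 0:

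| Assumed margin (SDd) | 5% per side | 2.5% per side |
|---|---|---|
| 0.4 | 12% | 3% |
| 0.5 | 39% | 18% |
| 0.6 | 65% | 45% |
| 0.7 | 83% | 69% |
| 0.75 | 89% | 78% |
| 1.0 | 99% | 98% |

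Power of 80% is reached at 0.68 SDd (5% per side) or 0.76 SDd (2.5% per side). A simulation of 200,000 trials at 0.7 SDd gave 82.7% and 68.7%, in agreement with the table.

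Zero difference is the most favourable case. At a true difference of 0.2 SDd and a margin of 0.7 SDd, power falls from 83% to 68% (5% per side), or from 69% to 53% (2.5% per side).

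**5. A margin set after the results.** The smallest margin that passes is |D| + t·s/√n, which exists for every data set. If the observed mean were 1.0 SDd with s equal to SDd, any margin above 1.0 + 0.387 = 1.387 SDd (90% CI) or 1.0 + 0.468 = 1.468 SDd (95% CI) would pass. A margin fixed in advance holds the chance of a false equivalence claim to at most the per-side level. A margin fitted to the interval gives no such limit. This follows from the algebra and does not predict what the sponsor will do.

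**The case against.** The strongest defence is that the study is the first of its kind, says so openly in section 10.2, and exposes no participant to risk because every intervention is made on a computer model. That accounts for the missing power calculation, which needs an SD. It does not account for the missing margin, which is an engineering judgement about how much extra stress or strain is tolerable and needs no earlier trial. The methods citation does not fill the gap either, because the plan adopts no margin from it. I could not see the figure in section 3 or the flow diagram in section 5, but no section refers to either for a margin. The absence of participant risk is fair context, but the validity of the only formal conclusion is still affected.

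Four stronger readings are tempting, and the documents do not support them.

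- **The treatment of lower values is undefined.** A reader might infer this from the question "Is the ToKa procedure as safe as the most commonly used existing HTO procedure", which sounds one-directional. But the plan says equivalence and names TOST, so as written a markedly lower stress or strain with ToKa counts against equivalence. What remains is a tension with the wording of the question, which needs confirmation.
- **The significance level is wrong.** The 5% two-sided default can be applied as 2.5% per one-sided test with a 95% CI. It needs stating but is not an error.
- **Twenty pairs are too few.** With no margin and no SD, the documents support neither that reading nor its opposite.
- **The margin will be chosen to fit the results.** No section says so. The point is only that the plan leaves this possible.

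Within-patient pairing, by contrast, is already stated and is not part of the gap.

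**Conclusion.** The point stands as a gap in the primary analysis that must be closed: TOST is the only named test of the main question, and for both outcomes it lacks a margin, a scale and a decision rule. This rests on the text alone and needs no assumption.

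The size depends on assumptions. The power figures assume normally distributed paired contrasts, margins expressed in units of an SD that the plan does not give, and no true difference unless stated. They show how strongly the meaning of 20 pairs depends on the missing number. They are not recommended margins and not an estimate of this study's power. The loss of error control applies only if the margin is set once results are known. The direction of the margin and the level per test are clarifications, not separate defects.

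**What to change.** Before any operated model is solved, add to section 10.3:

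1. The scale of the within-patient contrast, difference or log ratio ToKa/Tomofix, for stress and for strain.
2. A margin for each outcome, with an engineering justification that does not draw on the observed results.
3. The rule: equivalence is concluded only if the confidence interval of the paired contrast lies wholly inside the margin.

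Then report in section 10.2 what 20 pairs deliver at the chosen margin, for zero and non-zero true differences.

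Two clarifications belong in the same edit. First, confirm that markedly lower stress or strain with ToKa is meant to count against the conclusion; otherwise test only the upper bound and word the claim as non-inferiority. Either choice can be defended if fixed in advance. Second, state the level per one-sided test: 2.5% (95% CI) keeps the default, while 5% (90% CI) needs a stated exception.

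The direct cost is a few sentences. The real cost is that the sponsor commits to a margin that the results may miss, and a tight margin may show that 20 pairs are too few. At an assumed margin of 0.5 SDd, 80% power at zero difference needs 36 pairs (5% per side) or 44 (2.5% per side), more than the 30 records requested. At 0.75 SDd it needs 17 or 21. An increase beyond 30 would use the ethics extension that section 10.2 already foresees.

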10.2. The Number of Participants

This study will use data from 20 patients, allowing paired comparison between each intervention in each virtual patient increasing the study power. There are no previous studies of this type to base a power analysis upon, thus the data will be critically evaluated and should increased numbers be required an extension to the ethics will be made. In order to generate the virtual cohort we will request ethics for anonymous re-use of imaging records for 30 patients, allowing for drop out due to issues with images or patient anatomy.

10.3. Analysis of Outcome Measures/Endpoints

Two one-sided test (TOST) procedure on the mechanical load variables. The primary outcome measure will be maximum mechanical stress (von Mises stress) in the device under physiological loading experienced during gait and stair function at a simulated six weeks post-operatively. The secondary outcome measure will be the maximum mechanical strain (von Mises strain) in the bone around the screws holding the HTO plates.

11. DATA MANAGEMENT

11.1. Access to Data

Direct access will be granted to authorised representatives from the Sponsor or host institution for monitoring and/or audit of the study to ensure compliance with regulations.

Additionally, Renishaw plc. will be granted access to anonymised data for the purposes of pre-operative planning software development specifically for and only relating to the ToKa device.

11.2. Data Recording and Record Keeping

Data will be stored according to University of Bath's research data storage policy

<http://www.bath.ac.uk/research/data/policy/research-data-policy.html>

Anonymised data stored by Renishaw plc. will be stored according to their data storage policy:

<http://www.renishaw.com/en/data-protection-statement--7425>

12. QUALITY ASSURANCE PROCEDURES

The study may be monitored, or audited in accordance with the current approved protocol, ICH GCP, relevant regulations and standard operating procedures.

13. ETHICAL AND REGULATORY CONSIDERATIONS

13.1. Declaration of Helsinki

The Investigator will ensure that this study is conducted in accordance with the principles of the Declaration of Helsinki.

13.2. Approvals

The protocol will be submitted to an appropriate Research Ethics Committee (REC), and host institution(s) for written approval.

The Investigator will submit and, where necessary, obtain approval from the above parties for all substantial amendments to the original approved documents.

13.3. Reporting

The CI shall submit once a year throughout the study, or on request, an Annual Progress report to the REC Committee, host organisation and Sponsor. In addition, an End of Study notification and final report will be submitted to the same parties.

13.4. Participant Confidentiality

The study staff will ensure that the participants' anonymity is maintained. The participants will be identified only by initials and a participant's ID number on the CRF and any electronic database. All

documents will be stored securely and only accessible by study staff and authorised personnel. The study will comply with the Data Protection Act, which requires data to be anonymised as soon as it is practical to do so.

14. PUBLICATION POLICY

The Investigators will be involved in reviewing drafts of the manuscripts, abstracts, press releases and any other publications arising from the study. Authorship will be determined in accordance with the ICMJE guidelines and other contributors will be acknowledged.

16. APPENDIX C: AMENDMENT HISTORY

Amendment No.	Protocol Version No.	Date issued	Author(s) of changes	Details of Changes made
1	Version_0_02_UoB	24/10/2017	[name], [name]	Anonymised data access will also be granted to Renishaw plc. who are now partners in developing ToKa software
2	Version_0_03_UoB	23/01/2018	[name]	Amended number of data sets access requested for
